1 INTRODUCTION

This statistical analysis plan provides guidelines for the final presentation and analysis of the primary and secondary objectives and outcomes for the LACTATE study.

2 BACKGROUND AND RATIONALE

Maternal sepsis can develop in pregnant women and women who have recently experienced pregnancy. Failure to rapidly recognise and treat maternal sepsis is a common factor identified in those women who die (1). In partnership with the WHO, the Global Sepsis Alliance, the UK Sepsis Trust, and other stakeholders, the study team developed the Fluids, Antibiotics, Source identification and control, Transfer and Monitoring (FAST-M) sepsis care bundle specifically for pregnant or recently pregnant mothers in a low resource setting, which should be acted upon in all women with suspected sepsis within one hour. However, there is still considerable uncertainty around the optimal "trigger" used to identify when further action is required by the health care team to prompt FAST-M initiation. A "trigger" should ideally be a sensitive measure that enables reliable and early identification of women who may benefit from the FAST-M bundle use. This needs to be balanced against the risks of an imperfect trigger resulting in false positives, impacting on already overstretched resources and distractions from other clinical priorities. Furthermore, there is the danger of over treatment if FAST-M is administered to patients who do not have sepsis.

Measurement of blood lactate forms a key part of sepsis management and risk stratification in current international guidelines from both National Institute for Health and Care Excellence (NICE) in the United Kingdom (UK) and the Surviving Sepsis Campaign. However, these guidelines were developed for non-pregnant populations in high income countries (2). It would be expected that in the substantially different population of pregnant women, in low-resource settings, that the test may perform differently.

The aim of the LACTATE study is to investigate if a lactate measurement has incremental benefit over conventional maternal vital sign assessment in the diagnosis of sepsis and identification of women at risk of severe morbidity or mortality in low resource settings. We will assess the diagnostic and prognostic accuracy of venous lactate measurement in maternity populations, in low resource settings, which is unknown.

3 OBJECTIVES

The primary objective is to evaluate the diagnostic accuracy of maternal venous lactate measurement in addition to maternal vital signs (at Day 0 and/or Day 1), in maternal sepsis in low-resource health facility settings in Malawi, Uganda and Pakistan.

Secondary objectives are to:

• evaluate the immediate diagnostic value of lactate testing at Day 0 in addition to maternal vital signs in maternal sepsis at Day 0 (reference standard at Day 0 only);

- assess the short-term predictive value of lactate testing at baseline, in addition to vital signs, for maternal sepsis at 24-hours (24-hour reference standard) in those without sepsis at baseline;
- explore if baseline venous lactate, in addition to vital signs, improves prediction of severe morbidity and mortality from infection;
- explore if the diagnostic accuracy of lactate in addition to maternal vital signs alone, varies by the pre-specified subgroups of pregnancy status (pregnant or post-delivery / post miscarriage / post-abortion), source of sepsis (genital tract or non-genital tract) and condition on admission (stable or critical);
- examine the effect of adjusting the threshold values for lactate assessment on the sensitivity and specificity of the index tests;
- explore the use of an alternative reference standard in which the Sequential Organ Failure Assessment (SOFA) score is modified to use maternity specific ranges for creatinine and platelet concentration.

4 STUDY POPULATION

4.1 STUDY SETTING

The study aims to recruit 500 pregnant or recently pregnant women who will be identified and recruited in low-resource health facility settings from sites in Malawi, Uganda and Pakistan. Sites were identified and selected in collaboration with the PI and ministries of health to ensure that the sites would be able to fulfil the requirements of the protocol including adequate participant numbers, representativeness and equity.

4.2 ELIGIBILITY

Inclusion criteria:

- 1. Women pregnant or within 6 weeks of the end of the pregnancy.
- 2. Women with a suspected or confirmed infection requiring in-patient care:
 - A. Any suspected or confirmed infection with or without organ-dysfunction.
 - B. Any clinical signs suggestive of infection (e.g., fever).
 - C. Request for any bodily fluid culture (blood, urine, cerebrospinal fluid, etc.) or swab specimens (nasopharyngeal, oropharyngeal, vaginal, endocervical) for the diagnosis of suspected infection (not routine sampling e.g., routine COVID-19 screening).
 - D. Non-prophylactic use of antibiotics or other antimicrobial drugs at admission or during hospital stay.
 - E. Any procedure for treatment of a suspected infection (e.g., wound exploration, evacuation of the uterus, laparotomy, etc.).
 - F. Any unexplained organ-dysfunction (i.e., organ dysfunction not attributable to an underlying cause).
- 3. Estimated age \geq 16 years.
- 4. Willing to provide a signed (and witnessed, if applicable) informed consent form.

- 5. Willing to be contacted if necessary.
- 6. Willing to have additional blood samples taken.

Exclusion criteria:

- 1. Women In active labour or within 2 hours of delivery are excluded as lactate is expected to be elevated by labour and childbirth.
- 2. Women with any non-severe, localised, or chronic infection (TB, HIV) or colonization (GBS).
- 3. Women undergoing only treatment with prophylactic antibiotics (for procedures, GBS).

4.3 SCREENING/RECRUITMENT DATA

The number of patients screened, the number of patients recruited and the number of screened patients not recruited will be summarized overall and by site. The numbers and reasons for non-recruitment will be reported in a table.

4.4 WITHDRAWAL/LOST TO FOLLOW-UP

Participants are free to withdraw from the study at any point, or a participant can be withdrawn by the Investigator (such as if a patient is later found to be ineligible). Some patients may be discharged prior to their Day 1 (24-hour) assessment, in which case they will lack a reference standard at this timepoint and therefore will not be included in the primary analysis. Follow-up until hospital discharge or death is required. The numbers of loss to follow-up and withdrawal over the duration of the study will be reported alongside reasons in a table. A STARD flow diagram will be produced to describe the flow of participants through the study. This will include information on the number (with reasons) of losses to follow-up, withdrawals and participants excluded/ineligible.

Some participants may be transferred to another hospital facility but not discharged. Every effort will be made to collect data about all participants until day 14 (or discharge or death, whichever is sooner) including those transferred.

5 STUDY METHODS

5.1 STUDY DESIGN

LACTATE is a prospective, multi-site, phase III test accuracy study in low-resource health facility settings. Pregnant women (or 6 weeks from end of pregnancy) with a suspected or confirmed infection will be recruited from sites across Malawi, Uganda and Pakistan. They will receive two blood tests at Day 0 (baseline) and Day 1 (22-36 hours). Lactate testing will be conducted, but the results will not be shared with the care teams and will have no influence on the critical care or treatment women receive. Daily (24 (-2 or +12) hours apart) samples will be collected from day 2 to day 14 (or until discharge from hospital or death of the participant), as well as routine key data variables from the health records and physical evaluations of the participants well-being (see Appendix 1).

5.2 INDEX TESTS

The three index tests being evaluated are:

- 1) Vital signs at Day 0 (see Table 1)
- 2) Vital signs at Day 0 + lactate at Day 0
- 3) Vital signs at Day 0 and Day 1 + lactate at Day 0 and Day 1

The vital signs will indicate sepsis if one or more of the thresholds listed in Table 1 are exceeded. A lactate >2mmol/L will indicate sepsis. For tests combining vital signs and lactate, both will need to indicate sepsis to give a positive test result. For the test combining Day 0 and Day 1 measurements, a positive test will require the vital signs and lactate measurements to indicate sepsis at either Day 0 or Day 1.

Vital sign	Threshold
Respiratory Rate	>25 per minute
Heart rate	>120 beats per minute
Systolic Blood Pressure	< 90mmHg
Urine output	Less than 0.5ml/kg/hour
Mental state	Altered state

Table 1: Vital sign threshold values

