5.4 OUTCOME DEFINITIONS

The primary outcomes are the absolute differences in sensitivity and specificity between pairs of index tests: vital signs (Day 0) vs vital signs (Day 0) + lactate (Day 0), and vital signs (Day 0) + lactate (Day 0) vs vital signs (Day 0 and Day 1) + lactate (Day 0 and Day 1).

Secondary outcomes include:

- The absolute differences in sensitivity and specificity between vital signs (Day 0) alone and vital signs (Day 0) + lactate (Day 0) for maternal sepsis assessed at Day 0 only;
- The predictive value of vital signs (Day 0) alone compared to that of vital signs (Day 0) + lactate (Day 0) in those without sepsis at baseline, for maternal sepsis assessed at Day 1 only;
- The predictive value of vital signs (Day 0) alone compared to that of vital signs (Day 0) + lactate (Day 0) for the occurrence of severe morbidity and mortality from infection (WHO "severe maternal outcomes") (4), which is assessed daily until day 14 or discharge or death, if sooner;
- The sensitivity and specificity of vital signs (Day 0) + lactate (Day 0) and vital signs (Day 0 and Day 1) + lactate (Day 0 and Day 1) by: pregnancy status (pregnant or postdelivery/post miscarriage/post-abortion), source of sepsis (genital tract or nongenital tract) and condition on admission (stable or critical);
- The sensitivity and specificity of the primary index test comparisons including those women discharged early, assuming that they did not have sepsis;
- In an exploratory analysis, the sensitivity and specificity of each index test will be estimated based on different threshold values for lactate;
- To explore the use of an alternative reference standard, in which the SOFA score is modified to use maternity specific ranges for creatinine and platelet concentration, an independent expert review group will examine all cases with discordant results to adjudicate based on clinical features, clinical management, response to treatment and outcomes, if the case fitted the WHO definition of maternal sepsis. The pattern of discrepant results will be investigated descriptively.
 - 5.5 SAMPLE SIZE

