We aim to recruit 500 women to the study in total. In computing sample sizes, we estimated that an increase of 20% in sensitivity would be both feasible and clinically important. This equates to detecting an additional sepsis case for every 5 women who have sepsis. Assuming a prevalence of 40%, defining statistical significance at the 5% level and ensuring 90% power, up to 346 participants in total would ensure we are appropriately powered across a range of baseline sensitivities between 30 and 60% when vital signs alone are used. It is important to also estimate specificity to detect any important increase in false positives. With 200 patients without sepsis, the specificity of each test will be estimated with 95% confidence interval (CI) width of 15 percentage points for a specificity of 75% and width less than 10 percentage points for a specificity of 90%. This is adequate precision to allow important changes to be estimated. Allowing for loss to follow-up and missing / laboratory results, we consider an initial sample size of 500 as appropriate to allow the study to have adequate power to test these hypotheses. This number of cases will be feasible to collect within 12 months, based on current infection rate data from all sites.

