7.3 FINAL ANALYSIS

Primary analysis

We will estimate the sensitivity, specificity, positive predictive value (PPV) and negative predictive value (NPV) of the three index tests to detect sepsis assessed at Day 0 and Day 1. The 95% CIs for the estimates will be calculated using the Wilson method for proportions. To compare the accuracy of sepsis diagnosis by vital signs alone versus vital signs + lactate, we will fit separate generalized estimating equation (GEE) models for women with and without sepsis to estimate absolute differences in sensitivity and specificity, respectively. This approach exploits the paired nature of the data. We will compute absolute differences

in sensitivities and specificities from the GEE models using a post-estimation procedure with Cls computed using the delta method.

Secondary analyses

We will assess (a) index tests based on Day 0 only against Day 0 reference standard to determine immediate diagnostic value; (b) index tests based on Day 0 only against Day 1 reference standard in those without sepsis at baseline to determine short-term predictive value; and (c) index tests based on Day 0 only with occurrence of infection related "severe maternal outcome" (near miss or maternal mortality) (4) prior to hospital discharge to determine predictive value for severe morbidity or mortality (5) assuming that those women discharged prior to the Day 1 assessment did not have sepsis. Sensitivity, specificity, PPV, and NPV will be calculated for each test. In addition, for each of the analyses above, we will estimate absolute differences in sensitivity and specificity of vital signs alone versus vital signs (Day 0) + lactate (Day 0).

Pre-specified subgroup analyses will include pregnancy status (pregnant or postnatal) and illness severity to explore if the test accuracy of lactate in addition to vital signs alone varies by these subgroups.

Exploratory receiver operating characteristic (ROC) curve analyses will examine the effect of adjusting the threshold value for lactate on the sensitivity and specificity of the index tests.

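### The both-positive rule for vital signs + lactate excludes the 20-point sensitivity gain over vital signs alone on which the SAP sizes the study

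*SAP*

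**What the plan says.** SAP 5.2 gives one rule for vital signs, used inside all three index tests: "The vital signs will indicate sepsis if one or more of the thresholds listed in Table 1 are exceeded". For lactate it says "A lactate >2mmol/L will indicate sepsis". The two are joined as follows: "For tests combining vital signs and lactate, both will need to indicate sepsis to give a positive test result". For the third index test, which uses both days, "a positive test will require the vital signs and lactate measurements to indicate sepsis at either Day 0 or Day 1".

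SAP 5.4 names two primary pairs: "vital signs (Day 0) vs vital signs (Day 0) + lactate (Day 0), and vital signs (Day 0) + lactate (Day 0) vs" the Day 0 and Day 1 version of the combined test. Only the first pair has vital signs alone as comparator.

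SAP 5.5 then bases the sample size on a gain: "we estimated that an increase of 20% in sensitivity would be both feasible and clinically important". It explains this as one more case found for every five women with sepsis, so the 20% is absolute. The baseline is a sensitivity of 30% to 60% for vital signs alone. Prevalence is 40%, significance 5%, power 90%, and the result is up to 346 participants. On the other axis it says: "It is important to also estimate specificity to detect any important increase in false positives".

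**The concern.** Section 5.2 defines a combined test that can only be stricter than vital signs alone. Section 5.5 plans for a combined test that finds more cases and may raise more false alarms. These are opposite expectations for the same primary comparison.

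If the plan is followed as written, the definition of the test settles the direction of the first primary result: lactate loses or ties on sensitivity, and gains or ties on specificity. A reader could take that as evidence about lactate when it follows from the rule. The 90% power statement would also stand beside a comparison that cannot show the effect it was calculated for. Choosing the combining rule after the data are seen could reverse the sign of the result, so it has to be settled beforehand.

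**Working it through.** **Inputs.** Combining rule, vital-sign rule and lactate threshold: SAP 5.2. Primary pairs: SAP 5.4. Gain d = 0.20, baseline 30% to 60%, prevalence 0.40, power 90%, stated total 346: SAP 5.5. Two-sided 5%: SAP 6.1. Paired analysis: SAP 7.3. The SAP names no sample-size formula, so the formulas below are assumptions.

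**1. The plan's own figure.** For paired tests, let p01 be the share of cases positive on the combined test only, p10 the share positive on vital signs only, and ψ = p01 + p10. The number of cases is

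n = [1.960·√ψ + 1.282·√(ψ − d²)]² / d².

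If the two tests are taken as independent among cases, baselines of 30%, 40%, 50% and 60% need 127, 132, 127 and 111 cases. The largest need is at 40%, where p01 = 0.60 × 0.60 = 0.36, p10 = 0.40 × 0.40 = 0.16 and ψ = 0.52:

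- n = [1.960·√0.52 + 1.282·√0.48]² / 0.04 = 132.4 cases, and 132.4 / 0.40 = 331 women.
- With a continuity correction of 1/d = 5: 137.4 cases, about 343 women (345 if cases are first rounded up to 138).
- An unpaired two-proportion formula with continuity correction (40% vs 60%): about 139 cases, 348 women (350 if rounded up to 140).

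Both corrected versions come close to 346, which corresponds to 346 × 0.40 ≈ 138 cases.

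**2. What the rule in 5.2 allows.** Write V for Day 0 vital signs positive and L for Day 0 lactate positive. Test 1 is V. Test 2 is V and L, which is a subset of V. Therefore p01 = 0, and

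- sensitivity(test 2) − sensitivity(test 1) = −p10 ≤ 0;
- false positives(test 2) ≤ false positives(test 1).

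This holds for any data and any lactate threshold. Lowering the threshold can at most bring test 2 back to test 1. The paired calculation in step 1 needs p01 = 0.36; the rule fixes it at 0.

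**3. Size, by illustration.** Assume lactate is independent of vital signs among cases, with the sensitivities shown:

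| Lactate sensitivity (assumed) | Change at baseline 30% | Change at baseline 60% |
|---|---|---|
| 50% | −15 points | −30 points |
| 70% | −9 points | −18 points |
| 90% | −3 points | −6 points |
| 100% | 0 | 0 |

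Under any dependence the upper bound is 0.

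**4. The third index test.** It is positive if the joint criterion is met on either day, so it contains test 2 and can exceed it. With 70% lactate sensitivity and a baseline of 30%, test 2 has sensitivity 0.30 × 0.70 = 21%. A 20-point gain over test 2 then needs 0.20 / 0.79 = 25% of the remaining cases to turn positive on Day 1. At a baseline of 60% it needs 0.20 / 0.58 = 34%. Test 3 could also exceed Day 0 vital signs, but SAP 5.4 does not list that pair.

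**5. Figures for the two ways out.**

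- *Either component positive.* Now p10 = 0, and a 20-point gain means p01 = ψ = 0.20: n = [1.960·√0.20 + 1.282·√0.16]² / 0.04 = 48.2 cases, or 48.2 / 0.40 = 121 women. With the 1/d correction: 53.2 cases, 133 women. To reach +20 points, lactate must be positive in 0.20/0.70 = 29% (baseline 30%) to 0.20/0.40 = 50% (baseline 60%) of the cases that vital signs miss.
- *Both components positive.* With 138 cases, a 10-point loss has a Wald-type 95% CI of 0.10 ± 1.960·√(0.10 × 0.90 / 138) = 0.10 ± 0.050, roughly 5 to 15 points.

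**The case against.** The strongest reply is that the both-positive rule may be deliberate. SAP section 2 wants sensitivity balanced against false positives in overstretched services, and a stricter trigger serves the second aim. Testing is two-sided, so a loss can be detected. With about 138 cases and discordance in one direction only, power for a 20-point difference exceeds 99.9% by exact McNemar. That covers a loss in the first pair and a gain in the second. This stands, and it limits the point to the hypothesis stated in 5.5 and its direction. It does not remove the conflict: 5.5 specifies a gain over vital signs alone and gives no acceptable loss.

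Three stronger readings are tempting, and the SAP does not support them:

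- *That no analysis in the plan can show a sensitivity gain, or that its power is void throughout.* The third index test can gain over the second through Day 1 positives. It does not rescue 5.5, whose baseline is vital signs alone.
- *That 346 proves the authors assumed discordance in both directions.* An unpaired formula comes about as close, and no formula is named. How 346 arose is inference.
- *That the threshold analysis in 7.3 is a further error.* The SAP says only: "Exploratory receiver operating characteristic (ROC) curve analyses will examine the effect of adjusting the threshold value for lactate". A lower threshold can raise the combined test's sensitivity relative to its own version at 2 mmol/L. It simply cannot lift the Day 0 combined test above Day 0 vital signs. The analysis uses whichever rule is chosen.

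**Conclusion.** The conflict is real and confined to the first primary comparison. Under 5.2 the Day 0 combined test cannot exceed Day 0 vital signs in sensitivity or in false positives, while 5.5 plans for a 20-point rise in the first and watches for a rise in the second. The maximum possible gain is 0 points, so no sample size gives power for the stated effect on this pair.

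The conclusion needs only that both tests are scored in the same women from the same Day 0 vital signs, as the paired analysis in 7.3 intends. It does not depend on how 346 was derived or on the illustrative lactate sensitivities. Nothing else in the SAP resolves the conflict or shows which section reflects the intention. It needs correcting before analysis.

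**What to change.** Reconcile 5.2 and 5.5 before any accuracy data are analysed. The SAP gives no ground for preferring either of two options.

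1. **If a sensitivity gain is the intended hypothesis:** define the combined index test as positive when vital signs or lactate indicates sepsis. Keep the both-positive rule as a pre-specified secondary test. Restate power for one-directional paired discordance: for 20 points, about 48 cases (121 women) without continuity correction or about 53 (133 women) with it.
2. **If the both-positive rule is intended:** remove the 20-point gain and the reference to more false positives. State the question as specificity gained against sensitivity lost, with an acceptable loss fixed in advance. Restate 5.5 as precision, for example a 95% CI of roughly 5 to 15 points around a 10-point loss with 138 cases.

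Use the chosen rule in the exploratory threshold analysis as well.

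The cost is wording in 5.2 and a recalculated paragraph in 5.5, plus a matching edit to the protocol if it carries the same rule. Both options use measurements already planned, so no new data or patients are needed.

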5.3 REFERENCE STANDARDS

The reference standard for diagnosis of maternal sepsis is defined by Sepsis-3 criteria (3): women with both (i) suspected maternal infection and (ii) organ dysfunction, which will be identified by a SOFA score ≥2. Maternal sepsis will be assessed at Day 0 (sample 1) and Day 1 (sample 2) (22-36 hours after sample 1 is taken). Women will be diagnosed as having sepsis if they meet the criteria at either time point. If a woman dies due to infection prior to the 24-hour repeat sample, this death will be assumed to have been preceded by sepsis and will also be attributed as a sepsis related death. There is the potential for some women to be discharged prior to their Day 1 assessment. If this occurs, they will lack a reference standard at this timepoint and so will not be included in the primary analysis. However, these women with early discharge will be included in a sensitivity analysis which assumes that they were discharged because they were well and therefore did not have sepsis.

For the secondary outcome exploring if Day 0 venous lactate in addition to vital signs, improves prediction of severe morbidity and mortality from infection, the reference standard is the WHO "severe maternal outcomes" (4) which comprises of maternal death and organ specific complications ("near misses") (see Appendix 2).

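### Women discharged before Day 1 are excluded, then coded as not septic, with no exception for those already septic by their Day 0 SOFA score

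*SAP*

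**What the plan says.** Section 5.3 defines the reference standard as suspected maternal infection with "organ dysfunction, which will be identified by a SOFA score ≥2". It is assessed at Day 0 and Day 1, and the two are joined by an either/or rule: "Women will be diagnosed as having sepsis if they meet the criteria at either time point".

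For women who go home before Day 1, section 5.3 says "they will lack a reference standard at this timepoint and so will not be included in the primary analysis", and section 4.4 repeats the rule. A sensitivity analysis brings these women back and "assumes that they were discharged because they were well and therefore did not have sepsis". Section 5.4 lists the same analysis as a secondary outcome, "including those women discharged early, assuming that they did not have sepsis".

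Two other parts of the plan bear on this:

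- Section 7.3, analysis (a), sets "index tests based on Day 0 only against Day 0 reference standard to determine immediate diagnostic value", so the Day 0 reference result is treated as usable by itself.
- Section 7.3 ends the description of analysis (c), on severe maternal outcome, with "assuming that those women discharged prior to the Day 1 assessment did not have sepsis".

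The only stated exception concerns deaths from infection before the repeat sample, which section 5.3 counts as sepsis.

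**The concern.** Under an either/or rule, a Day 1 result can add a case but cannot remove one. The stated reason for exclusion, no reference standard at Day 1, therefore leaves a woman unclassified only if she was negative at Day 0. For a woman with Day 0 SOFA of 2 or more, the plan discards a known case from the primary analysis and then, as worded, overwrites her observed positive result in the sensitivity analysis.

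Three things are at stake:

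- The sensitivity analysis would contain misclassification of its own making, so it could not show cleanly whether early discharge matters.
- Both analyses leave these cases out of the sensitivity estimate. If they are milder cases that the tests miss more often, sensitivity is overstated.
- The first primary comparison, vital signs alone (test 1) against vital signs plus lactate (test 2), uses Day 0 index data only. These women have all that is needed for its sensitivity half.

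**Working it through.** **1. The rules side by side.**

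| Discharged before Day 1 | Status by the either/or rule | Primary analysis | Sensitivity analysis, read literally | Analysis (a), Day 0 reference |
|---|---|---|---|---|
| Day 0 SOFA ≥2 | Septic, settled | Excluded | Not septic | Septic |
| Day 0 SOFA <2 | Not known | Excluded | Not septic (assumed) | Not septic |

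The second row is coherent. The first is not: the same woman can be a case in analysis (a) and a non-case in the sensitivity analysis.

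**2. Power is not the issue.** The SAP gives no early-discharge figure to reproduce. Its 346 participants (section 5.5) can be approximated at the worst case, 40% against 60% sensitivity, two-sided 5%, 90% power. Formulas with a continuity correction give 344 to 356 in total; those without give 325 to 333. At 40% prevalence, 346 × 0.40 ≈ 138 septic women. In the illustrations below at least 160 remain, so the problem is bias.

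**3. One scenario.** From the SAP: N = 500 and 40% prevalence, applied here to women who stay. Assumed: 10% discharged early (E = 50), 20% of them positive at Day 0 (m = 10), and vital-sign sensitivity 50% and specificity 75%. Then 450 stay, 180 of them septic and 270 not.

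Apparent specificity = [(270 + 50 − 10) × 0.75 + 10 × (1 − 0.50)] / (270 + 50) = (232.5 + 5) / 320 = 74.2%, against 75%.

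**4. Range.** The same formula over the assumed ranges:

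| Early discharge | Day 0-positive among them | Women miscoded | Share of known septic women | Apparent specificity |
|---|---|---|---|---|
| 5% | 5% | 1.25 | 1.25/191.25 = 0.7% | 74.9% |
| 10% | 20% | 10 | 10/190 = 5.3% | 74.2% |
| 20% | 40% | 40 | 40/200 = 20% | 72.1% |

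**5. The paired difference.** Section 5.4 makes differences the primary outcomes, so these matter more than single-test values. Let w be the miscoded share of the specificity denominator. The apparent specificity difference (test 2 minus test 1) is (1 − w) × (true specificity gain) + w × (sensitivity of test 1 minus test 2 among the miscoded women).

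- With assumed specificity 75% to 90% and sensitivity 50% to 35%, both terms are 15 points, so there is no shift at any w. That is a coincidence of the inputs.
- If the miscoded women score the same on both tests, the second term is zero. With w = 10/320 the difference is 0.969 × 15 = 14.5 points; with w = 40/340 it is 0.882 × 15 = 13.2 points.

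**6. Sensitivity.** Assume 200 septic women with 60% sensitivity overall, of whom k are Day 0-positive early leavers testing positive 40% of the time. Leaving them out gives (120 − 0.4k)/(200 − k): for k = 5, 10, 20, this is 60.5%, 61.1%, 62.2%. If they test positive 60% of the time, there is no shift.

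**7. Prevalence under each rule**, in the scenario of step 3, supposing the other 40 early leavers never become septic:

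- full cohort, true: 190/500 = 38.0%
- primary analysis as planned: 180/450 = 40.0%
- sensitivity analysis read literally: 180/500 = 36.0%
- keeping early leavers only if positive at Day 0: 190/460 = 41.3%

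The last line shows that simply returning Day 0-positive women to the primary set would move prevalence, and with it PPV and NPV, further from the truth.

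**The case against.** The best defence is that the missing result is expressly the one at Day 1, so the sensitivity analysis may intend only to fill that gap with no sepsis at Day 1, leaving Day 0 to decide. This is a fair reading, and it rules out saying that every such woman is misclassified with certainty. But the assumption in 5.3 and 5.4 carries no time limit, and this reading does not touch the primary-analysis exclusion.

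That exclusion also has a rationale. Test 3 needs Day 1 vital signs and lactate, so restricting to women with Day 1 data gives a common set. This stands for test 2 against test 3, but not for test 1 against test 2.

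Some stronger inferences are tempting but unsupported:

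- *Every missing Day 1 assessment is treated this way.* The rule covers discharge only. Infection deaths count as sepsis, and no coding rule is stated for other missing Day 1 samples.
- *The interim sample-size review is distorted.* Section 7.2 does not say how early leavers enter the prevalence estimate, and it provides for a review of women without a Day 1 assessment.
- *Analysis (c) is biased.* Its outcome is the observed severe maternal outcome, which a sepsis label does not alter. The trailing clause looks misplaced; no bias is shown.
- *The primary differences are shown to be wrong.* Step 5 shows that the specificity difference in the sensitivity analysis can shift a little or not at all. Any shift in sensitivity depends on how these women test, which is unknown.

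**Conclusion.** The point holds in a limited form. The either/or definition in 5.3 conflicts with the handling of women discharged before Day 1 who had Day 0 SOFA of 2 or more. Their exclusion from the primary analysis is unambiguous; their coding as non-cases in the sensitivity analysis follows from the literal wording.

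The size is unknown, because the SAP gives neither the early-discharge rate nor these women's Day 0 status. Over the assumed ranges, 1 to 40 women are affected and apparent specificity falls by 0.1 to 2.9 points. Under the inputs of step 5, the specificity difference shifts by 0 to 1.8 points. If few women septic at Day 0 go home early, the effect is small. The rule still needs correcting before analysis: programmed literally it overwrites observed results, and programmed charitably it departs from the text.

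**What to change.** - **5.3 and 5.4, sensitivity analysis.** State that women discharged early keep their Day 0 reference result, and that no sepsis at Day 1 is assumed only for those with Day 0 SOFA below 2.
- **4.4, 5.3 and 7.3, test 1 against test 2.** Retain Day 0-positive early leavers as cases in the sensitivity comparison. Section 7.3 already fits separate models for women with and without sepsis, so the specificity model is unchanged. Women with Day 0 SOFA below 2 and no Day 1 result remain unclassified and outside the primary analysis.
- **PPV, NPV and prevalence.** Take these from the corrected full-cohort sensitivity analysis, since retention that depends on the Day 0 reference result inflates prevalence.
- **Test 2 against test 3.** Keep the set with Day 1 data as primary. Report scoring of test 3 on Day 0 alone as a sensitivity analysis, noting that it makes tests 2 and 3 identical for early leavers and pulls the difference toward zero.
- **7.3.** Move the no-sepsis clause from analysis (c) to the early-discharge sensitivity analysis.

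The cost is a few sentences and a modest change to the derivation rules. The downside is slightly different analysis sets for the two primary comparisons, which the report should state.
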